**INSTRUCTIONS:**

- Complete this Protocol Template only when there is **no** existing authored protocol provided for this study.
- If you are doing a data-only study with no prospective or interventional components, use the Data Only Protocol Template instead.
- This Protocol Template is to be used in conjunction with the SMART KP IRB Core Data Form.
- Enter your responses to each question directly below the **BLUE** text in the fillable field.
- When completing this Protocol Template, if a section does not apply to your study then enter "N/A."

**2. Objectives**

Describe in plain language the purpose, specific aims, or objectives and indicate the primary goal(s) of the study (e.g. safety, tolerability, effectiveness, feasibility, pilot study, etc.). State the hypotheses to be tested. State primary and any secondary study endpoints.

This study will adapt and test a University of Washington (UW) developed/piloted pain self-management training for prescription opioid taper intervention at Kaiser Permanente Washington (KPW). To address patients' fears of opioid taper that limited recruitment into our pilot study, we will begin with randomization to pain self-management training and then offer the option of self-paced opioid taper: *Pain Self-Management Training for Opioid Taper* (PSMOT). The optional taper will occur through recommendations from the research interventionist the patient's primary care provider (PCP). This study aims to enroll 250 participants and randomize them into either 1) a nurse or physician assistant research interventionist guided PSMOT or 2) regular care (no intervention). Specifically, we will test the effectiveness of this intervention, compared with control group on opioid dose and pain outcomes among patients on high dose ( $\geq$  40 mg morphine equivalent dose) long-term opioid therapy (LtOT) for chronic non-cancer pain (CNCP) in a pragmatic randomized trial.

The objectives of this study are:

- To adapt our previously developed prescription opioid taper support intervention by a physician assistant into a telephone-delivered pain self- management training that provides the option for supported opioid taper (PSMOT) through the patient's PCP. We will recruit participants who receive care from multiple primary care clinics. The intervention will be administered by a KPWA research interventionist (a physician assistant or registered nurse) who will be trained and supervised by a UW pain psychiatrist and UW research clinician and will include guidance in opioid and non-opioid medication prescribing. This training and guidance will be consistent with KPWA guidelines.
- To test in a randomized trial the effects of this PSMOT intervention on: **a) opioid outcomes**: daily opioid dose (*primary outcome*), percent dose reduction from baseline, problem opioid use (interview, questionnaire, and electronic health record text indicators), and patient-reported opioid problems; and **b) pain-related outcomes**: PEG (self-report of Pain intensity, Enjoyment of life interference, General activity interference - *primary outcome*), pain self-efficacy, and depression symptoms

We will test the effectiveness of this intervention, compared with control group, on opioid dose and pain outcomes among patients on high dose ( $\geq 40$  mg morphine equivalent dose) LtOT for CNCP in a pragmatic randomized controlled trial. This intervention will have two components:

- telephone-delivered evidence-based pain self-management training with supplemental materials including:
  - A participant workbook
  - *The Pain Survival Guide book*
  - Audio files of relaxation techniques (these will be available both as in a CD format and we are working with Eagles to create a study website that will host these files. : [www.stripestudy.org](http://www.stripestudy.org)
  - A web-based video of successfully tapered patients with motivational *interviewing* debriefing: [www.stripestudy.org](http://www.stripestudy.org)
- Voluntary, self-paced opioid taper through recommendations to the PCP
  - Including opioid and non-opioid prescribing guidance from the research interventionist to the patient's PCP.

**Hypotheses pertaining to opioid use:** Patients receiving LtOT for chronic non-cancer pain (CNCP) randomized to the PSMOT intervention, as compared with those randomized to a control group, will have lower opioid doses, greater percent reduction of opioid dose, lower proportions with problem opioid use, and lower levels of patient-reported opioid-related problems at 6 and 12 months after randomization.

**Hypotheses pertaining to pain outcomes:** Patients receiving LtOT for CNCP randomized to the PSMOT intervention, as compared with those randomized to the control arm, will have lower PEG scores, higher levels of pain self-efficacy, and lower levels of depressive symptoms at 6 and 12 months after randomization. The proposed trial will determine whether pain self-

management training can promote prescription opioid taper in higher-dose long-term opioid therapy patients without increasing pain levels or activity interference. If this trial is successful, *then prescribers and patients may be able to pursue supported opioid taper without fear of escalating pain.*

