### 3. Background

#### a. Scientific Background

Provide the scientific or scholarly background for, rationale for, and significance of the research based on the existing literature and how will it add to existing knowledge. A list of references or bibliography must be included as part of this document or uploaded separately.

The evidence that LtOT improves chronic pain and function in patients with CNCP is weak, but there is strong evidence of dose-dependent risk for serious harms such as opioid abuse, Opioid Use Disorder (OUD), overdose, and death. LtOT patients are a high-risk group with high rates of substance use, mental disorders, problem opioid use, and adverse effects of opioids, including OUD, overdose, and death. Rapid opioid detoxification of these LtOT patients may lead to illicit opioid use, but gradual, supported opioid taper may reduce risks of opioid adverse events. While many LtOT patients are interested in opioid taper or discontinuation, they also fear increased pain. In a previous, NIDA-funded R34 pilot study of prescription opioid taper support, this study PI demonstrated that over 18 weeks opioids can be tapered more effectively than in control arm (43% vs 19% dose reduction) with no increase in pain intensity and significantly reduced activity interference for those receiving taper support. We have been funded by the National Institute on Drug Abuse (NIDA) to study this intervention in the KPWA delivery system. See grant proposal for bibliography.

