#### 4. Study Design

Describe the overall approach of the study (e.g. prospective, interventional, observational, retrospective, etc.). If your study includes more than one group, arm, or subject population, describe that here (for example, a study of both subjects and their caregivers, or a study with **both a prospective interventional arm and a retrospective chart review arm**).

This study is a pragmatic randomized trial that includes data collected from electronic health records (EHR – KPWHRI Virtual Data Warehouse), patient self-report, and data on the training sessions. There are two arms in the trial: a research interventionist guided Pain Self-Management Opioid Taper (PSMOT) or control group (no intervention, usual care). In addition, the education intervention has a sub-arm which involves an opportunity to taper opioid medication dosing. The goal of the tapering is to gradually decrease opioid dosing by ~ 10% per month.

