#### Secondary data: data, sources, and date range

In addition to the primary data described above, secondary data to be collected on participants enrolled in both arms of the study are listed in the table below.

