#### Data from KP Washington

Source (specify) (i.e., from KPWA, or from an existing or previous study)	Key Information/Description of Variables	Date Range
KPWA data sources (VDW)	Diagnoses via ICD codes and dates of code: Comorbidities (comorbidity indices and the individual constituent diseases), mental health disorders (e.g. depression, anxiety), substance use disorders (e.g. opioid use disorder, alcohol use disorder, tobacco use disorder, cannabis use disorder, stimulant use disorder),	2016-2022

	cancer, suicidal ideation, and pain including site of pain	
KPWA data sources (VDW)	Social history table variables for alcohol use and tobacco use	2016-2022
KPWA data sources (VDW)	Health plan enrollment information (start and stop dates)	2016-2022
KPWA data sources (VDW)	Health care utilization including: outpatient, inpatient, emergency department	2016-2022
KPWA data sources (VDW)	Medication orders and pharmacy dispensings including dates	2016-2022
KPWA data sources (VDW)	Laboratory tests and results	2016-2022

DIRECT IDENTIFIERS			
 Names  Dates  Postal address  Geocode  Phone numbers  Fax numbers  Email address	 Social Security Numbers  Medical record numbers  Health plan numbers  Account numbers  License/Certificate numbers  Vehicle ID numbers  Device identifiers/Serial numbers	 Web URLs  IP address numbers  Biometric identifiers (e.g., finger prints, voice prints, retina scans)  Facial Photos/Images  CHS ID  Other unique identifier(s):	

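### The EHR-text component of problem opioid use has no listed data source, and overdose, suicide attempt and death have no systematic source common to both arms

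*Combined protocol and SAP*

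**What the plan says.** **The outcome.** Section 2 (Objectives) lists among the opioid outcomes "problem opioid use (interview, questionnaire, and electronic health record text indicators". The matching hypothesis expects "lower proportions with problem opioid use" in the intervention arm at 6 and 12 months.

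**The data.** Section 4 (Study Design) describes the trial's sources as "data collected from electronic health records (EHR – KPWHRI Virtual Data Warehouse), patient self-report, and data on the training sessions". Section 6, in the part that covers both arms, states that "secondary data to be collected on participants enrolled in both arms of the study are listed in the table below". The table has six rows: ICD diagnoses, social history (alcohol and tobacco), enrolment start and stop dates, utilisation, medication orders and dispensings, and laboratory tests. The diagnosis row includes "substance use disorders (e.g. opioid use disorder, alcohol use disorder, tobacco use disorder" and ends with "cancer, suicidal ideation, and pain including site of pain". The utilisation row reads "Health care utilization including: outpatient, inpatient, emergency department". The control-arm part of Section 6 adds no further data. The intervention-arm part adds the current problem list and medication list from Epic.

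**The harms.** Section 3.a motivates the trial by "dose-dependent risk for serious harms such as opioid abuse, Opioid Use Disorder (OUD), overdose, and death". Section 9.a names withdrawal symptoms as a risk for those who taper. Section 8 has staff record adverse events in the course of their contact with participants. The biostatisticians compare the groups once a year and report to the monitoring committee.

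**The concern.** Two gaps arise when the outcome and harms are set against the data to be collected.

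First, an outcome with three stated components has a listed source for at most two. An analyst who follows the table would have to drop the text component or improvise one after the data are in hand. Section 6.a gives a general model for dichotomous outcomes. It gives no rule for combining the three components or for proceeding when one is absent.

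Second, the most serious harms in the rationale would reach the between-arm comparison only if staff happened to learn of them, and staff contact differs greatly by arm. A yearly review whose purpose is to detect an excess of events in one group could show an excess that reflects more frequent questioning. It could also miss events among controls.

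**Working it through.** The plan gives no figure on this point, so the check is to place each needed item beside the both-arm table.

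| Item | Where the plan relies on it | In the both-arm table? |
|---|---|---|
| EHR text indicators | Section 2, secondary outcome | No |
| Interview and questionnaire measures of problem use | Section 2, secondary outcome | Not applicable; they come from instruments attached separately |
| Opioid use disorder diagnosis | Section 3.a, named harm | Yes |
| Overdose or poisoning | Section 3.a, named harm | Not named |
| Death | Section 3.a, named harm | Not named; enrolment stop date only |
| Suicidal ideation | Section 5.b, exclusion | Yes |
| Suicide attempt | Section 5.b, exclusion | Not named |
| Withdrawal | Section 9.a, taper risk | Not named |
| Inpatient and emergency use | General harms signal | Yes |

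**Can another listed source supply the text?** The Epic problem and medication lists are for the intervention arm only, and they are lists rather than notes. The identification pull in Section 5.b covers diagnoses, utilisation and procedures from the same warehouse, but it serves to find eligible people and also contains no text. Taper details in the intervention arm come partly from the medical record, but they concern the taper and have no control-arm counterpart. No both-arm text source is stated anywhere.

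**How unequal is the contact?** Section 4 gives the intervention arm up to 18 calls, and Section 6 provides for adverse events and critical incidents to be recorded at each. Both arms have three surveys, of which the baseline survey precedes randomisation.

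- Scheduled contacts after randomisation, intervention: up to 18 + 2 = 20.
- Scheduled contacts after randomisation, control: 3 − 1 = 2.
- The follow-up surveys may be completed on the web. For a participant who does so, scheduled staff contact is up to 18 against 0.

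**What does that do to the comparison?** Suppose the true event risk is r in both arms, and an event is captured with probability c₁ in the intervention arm and c₀ in the control arm. The recorded risks are r·c₁ and r·c₀. Their ratio is c₁/c₀, which exceeds 1 whenever capture is better in the intervention arm, even with no difference in true risk. The documents do not give c₁ or c₀, so the ratio cannot be quantified. Its direction follows if capture rises with contact. Conversely, equal recorded counts would not establish equal risk.

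**The case against.** The strongest reply is that the table is a summary. Its column is headed as key information, and its mental health and substance use groups are introduced as examples, so related codes may be pulled. Pregnancy codes are to be pulled for all participants although the table does not name them. However, the pregnancy pull is stated elsewhere in the protocol. A follow-up pull of note text, overdose codes, suicide attempt or death is stated nowhere. If one is intended, a short clarification settles the matter.

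It is also fair to say that overdose, suicide attempt and death are not stated outcomes. The case for listing them rests on the planned yearly harms comparison and the trial's own rationale.

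A reader might go further in four ways that the documents do not support:

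- *That the named harms cannot be counted in either arm.* Opioid use disorder, suicidal ideation, and inpatient and emergency use are listed for both arms. Adverse events and critical incidents are recorded at each intervention session, and Section 8 gives a route for serious events in either arm. One limit stands: participants using buprenorphine for opioid use disorder are removed from the analyses, which weakens counts of that diagnosis.
- *That problem opioid use cannot be measured at all.* The interview and questionnaire components are untouched by this table. Section 2 does not say whether the three sources form one composite or separate indicators.
- *That a death would show only as missing data.* An enrolment stop date, utilisation or a serious-event report may reveal it. What is lacking is a systematic source that separates death from leaving the plan.
- *That chart text is ruled out because the research physician will not abstract charts.* That statement concerns one physician's review of difficult cases and says nothing about outcome data.

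**Conclusion.** The point holds in a limited form. One of the three stated components of a secondary outcome has no stated data source. Overdose or poisoning, suicide attempt and death have no stated systematic source common to both arms. The yearly adverse event comparison therefore depends on contact that, after randomisation, is scheduled up to 20 times in one arm and twice in the other.

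This rests on two assumptions: that the both-arm table is followed as written, and that events are more likely to be recorded when staff speak with participants more often. The survey instruments are not available here. If they ask both arms the same questions about harms, the imbalance would be reduced for survivors who respond, but the surveys could not supply EHR text or deaths. The number of events affected cannot be estimated. Because neither co-primary outcome uses note text, this should be corrected but does not threaten the main comparison.

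**What to change.** 1. **Reconcile Section 2 with the both-arm table in Section 6.** Either add the EHR-text source and the method for deriving the indicators, for both arms, or redefine problem opioid use without the text component. Redefinition is the cheaper option.
2. **Extend the same table** with diagnosis codes for overdose or poisoning, opioid withdrawal and suicide attempt, and with date of death, using one window for both arms.
3. **In Section 8, base the between-arm harms comparison** on these same-source counts, both at the yearly review and at the end of the trial. Report contact-based adverse events separately, with the difference in contact stated.

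The cost is an IRB amendment to one data table, matching text in Section 8 (and in Section 2 if the outcome is redefined), and a slightly larger pull by the existing programmer. Adding note text would cost more. Coded data will miss events not seen or recorded in the health system, so they complement the contact-based reports and do not replace them.

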#### Primary Data Collected on the Intervention

During each telephone session, the research interventionist will track the phone sessions into the project REDCap tracking data base hosted at KPWA. The information captured at the visits includes:

- Date of the phone visit

- Whether or not the participant attended their scheduled appointment
- Check boxes for session content that was covered during the visit
- Any critical incidents (intent to harm oneself or other)
- Any adverse events
- Detailed notes on the visit
- Amount of time spent on each visit
- HADS and GCPS score ( score read to interventionist and entered into REDCap at the beginning of each session for participants who choose to taper)

At the fourth study visit, the research interventionist will ask participants if they want to taper their opioid dosing. If the participant declines to taper, they will proceed with the rest of their pain self-management sessions and follow-up surveys. If a participant expresses interest in tapering, the interventionist will recommend medication taper suggestion to the participant's PCP using Epic Telephone Encounters. We will provide taper support at a later date if they prefer to delay the taper or resume paused tapers. Patients will be allowed to pause tapers (i.e., put the taper on hold) for any reason including the need to escalate opioid dose (e.g., surgery requiring additional pain management). Patients delaying or pausing tapers will still continue to receive the pain self-management training. Participants will be informed of the risk of stock-piling opiates during the taper process. The research interventionist may need to consult with [name], the study research physician on complicated tapering scenarios. [name] will have Epic read only access to review the medical records of any difficult tapering sessions to provide guidance to the research interventionist. The guideline for tapering was developed by [name] (UW psychiatrist and Principal Investigator), and is attached. The guidelines were reviewed by [name] (KP Medical Director, Continuum of Care), [name] (Family Medicine Physician and Medical Director, Clinical Knowledge Development and Support), [name] (Family Medicine provider, Program Chief of Family Medicine, study Co-Investigator) and [name], BCACP (Pharmacy Clinical Coordinator, Quality and Clinical Operations). This taper guideline is consistent with KPWA guidelines for COT tapering.

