- The research interventionist will pass provide a medication recommendation to the PCP using Epic Telephone Encounters. Additionally, any study information that is collected as part of the telephone visit which the research interventionist feels may be important to either support the taper or supplements clinical care may be shared with the provider. This will continue through the course of the taper for patients electing to try the taper support.

c. Data and/or Specimen Banking

Indicate if specimens may be used for future research and whether that may include genetic research.

State if data or specimens will be sent to a separate repository. If data or specimens will be banked in a repository for future use as part of this protocol submission address the following questions:

- What will be banked and what identifiers will be associated with the data or specimens?
- Where and how will the data or specimens be stored?
- For what purpose will the data or specimens be used?
- How will the data or specimens be accessed, and who will have access?
- Describe the procedures to release data or specimens, including the process to request a release, approvals required for release, who can obtain data or specimens, and the data to be provided with specimens.

N/A we will be not banking data or specimens for this project

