**12. Resources Available**

Describe any special resources or expertise required to conduct the study.

[name], Senior Scientific Investigator at KPHRI, will spend .20 FTE conducting and completing this research. She will oversee all aspects of the study at KPW.

The project will use REDCap to collect data from participants and to track participant progress through the study.

Additionally, [name] is working closely with [name]. [name] is a Family Medicine provider and Program Chief of Family Medicine at KPW who assisted with developing and rolling out KPW's newest guidelines on chronic opioid therapy. She will serve as the liaison between the study team the KPW delivery system and KPW leadership. She will be the Study

Clinic Champion directly involved with educating providers, promoting the study, recruitment and retention.

[name] meets and touches based regularly with others in the KPWA delivery system including [name] (Medical Director, Continuum of Care), [name] (Family Medicine Physician and Medical Director, Clinical Knowledge Development and Support), and [name], BCACP (Pharmacy Clinical Coordinator, Quality and Clinical Operations). [name] keeps them apprised of the trial aims, design, and methods while they provide feedback on trial and keep her up to date on of KPW initiatives around safe opioid prescribing and tapering.

Finally, the taper portion of the study functions by working in conjunction with the participant's primary care provider. The research interventionist use Epic Telephone Encounters to pass on medication dosing recommendations to the primary care provider and any other research information that may be pertinent for the provision of health care.

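### Problem opioid use is read partly from chart text, and the trial itself adds opioid-related chart text in the intervention arm only, so ascertainment of this secondary outcome can differ by arm

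*Combined protocol and SAP*

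**What the plan says.** Section 2 lists the opioid outcomes. Daily dose is primary; among the others is "problem opioid use (interview, questionnaire, and electronic health record text indicators". The hypothesis in the same section is that the intervention arm will show "lower proportions with problem opioid use" at 6 and 12 months.

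Three places describe study staff communicating through the chart, all in connection with the intervention:

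- Section 6, Primary Data Collected on the Intervention: for a participant who expresses interest in tapering, taper suggestions go to the "PCP using Epic Telephone Encounters".
- Section 6.b, Sharing of Results with Subjects: the interventionist will "provide a medication recommendation to the PCP using Epic Telephone Encounters", and may also share "any study information that is collected as part of the telephone visit which the research interventionist feels may be important", through the course of the taper.
- Section 12, Resources Available: "The research interventionist use Epic Telephone Encounters to pass on medication dosing recommendations to the primary care provider", together with other research information thought relevant to care.

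The session table in Section 6 (session 4) tells interested participants to book a visit with their primary care provider (PCP) to discuss taper. Sections 4 and 5.k send the PCP a letter for intervention participants only. The control-arm procedures consist of surveys and no intervention visits.

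The table of secondary data for both arms (Section 6, Data from KP Washington) covers diagnosis codes, social history, enrollment, utilization, medications and laboratory results. It does not list note text. Section 6.a gives dichotomous secondary outcomes a modified Poisson model with baseline covariates and says nothing further about this outcome.

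**The concern.** An outcome found by searching chart text depends on how much relevant text the chart contains. Here the trial adds opioid-related text to some intervention charts and none to control charts. If any of that text trips an indicator, a participant is counted for a reason that comes from allocation and not from problem use.

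Baseline covariate adjustment does not repair outcome measurement that differs by arm. The robust variance does not help either, because the problem is bias and not precision. At stake is a safety-relevant secondary comparison: a real reduction could be hidden, or an apparent harm shown where none exists.

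**Working it through.** **Is there a figure to reproduce?** No. The documents give no prevalence, effect size or power for problem opioid use. The check is first a reading of the text and then an illustration.

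**Step 1: the two arms side by side.**

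| Source of opioid-related chart text | Intervention | Control |
|---|---|---|
| Usual-care notes | yes | yes |
| Study-written Epic encounters (taper, medication, other session information) | yes, mainly those interested in taper | none described |
| PCP visits prompted by the study to discuss taper | yes, those interested in taper | none described |
| PCP informed of allocation by letter | yes | no |

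The second and third rows exist only because of allocation. No section excludes them from the text search, describes arm-blind abstraction, or plans the outcome without text.

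**Step 2: illustration.** Let p be true prevalence, equal in both arms; Se the sensitivity; F the control false-positive rate; and e the extra false-positive rate averaged over the whole intervention arm.

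- Control observed: p × Se + (1 − p) × F
- Intervention observed: p × Se + (1 − p) × (F + e)

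Assumed, not from the documents: Se = 0.80, F = 0.05, p = 10% to 30%, e = 2 to 10 points. From Sections 5.a and 6.a: 125 per arm, or about 106 at 85% follow-up (125 × 0.85 = 106.25), and two-sided alpha 0.05.

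Worked case, p = 0.20 and e = 0.05:

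- Control: 0.20 × 0.80 + 0.80 × 0.05 = 0.20
- Intervention: 0.20 × 0.80 + 0.80 × 0.10 = 0.24
- Observed relative risk (RR) with no true effect: 0.24 / 0.20 = 1.20

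The chance of a nominally significant result uses d = difference in observed proportions, s0 = √(2p̄(1 − p̄)/n) with p̄ their mean, and s1 = the unpooled standard error: 1 − Φ((1.96·s0 − d)/s1) + Φ((−1.96·s0 − d)/s1). In the worked case with n = 106, d = 0.04, s0 = 0.0569 and s1 = 0.0568, giving 0.108.

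| e (points) | RR, p = 10% | RR, p = 20% | RR, p = 30% | Chance of p < 0.05 with no true effect (n = 106 to 125) | A true RR of 0.5 would appear as |
|---|---|---|---|---|---|
| 0 | 1.00 | 1.00 | 1.00 | 5% | 0.59 to 0.70 |
| 2 | 1.14 | 1.08 | 1.05 | 6% to 7% | 0.65 to 0.85 |
| 5 | 1.36 | 1.20 | 1.13 | 9% to 17% | 0.75 to 1.08 |
| 10 | 1.72 | 1.40 | 1.25 | 20% to 47% | 0.90 to 1.46 |

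Because e is an average over the arm, it shrinks with exposure. If half the arm had such entries and 10% of those otherwise negative were falsely flagged, e would be 0.5 × 10 = 5 points.

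The table shows only that modest arm-dependent error would matter. It does not estimate what will happen.

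**The case against.** **Exposure is partial.** The routine Epic message follows an expression of interest in tapering. Session notes, adverse events, critical incidents and taper tracking go to the REDCap tracking database and not to the chart. The wider sharing in Sections 6.b and 12 is discretionary. This stands, and it limits the mechanism mainly to the tapering subgroup.

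**Opioid text is not problem-use text.** A taper recommendation need not trip an indicator of problem use, and PCP replies are not guaranteed: the taper tracking allows for no response. This also stands. A reader might infer that the count in the intervention arm is certain to be inflated. The documents do not support that, because the indicators are undefined.

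**Larger figures are tempting.** If any positive source counts, sensitivity is perfect, controls have no false positives, and 5% to 20% of unflagged intervention participants are falsely flagged, then a 20% base rate gives (0.20 + 0.80 × 0.05) / 0.20 = 1.2 at the low end, and a 10% base rate gives (0.10 + 0.90 × 0.20) / 0.10 = 2.8 at the high end. None of those conditions is in the plan, so 1.2 to 2.8 should not be quoted as the size of the bias.

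**The data list omits note text.** If text is never pulled, the bias cannot arise. But then the outcome in Section 2 has no source for one of its components. Either way the plan needs correcting.

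**A rule may exist elsewhere.** The Communication Plan, Taper Guidelines, survey document and grant proposal are cited but not part of these documents. If one of them already handles study-written text, the analysis plan should say so.

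**Conclusion.** The point holds in limited form. As written, the plan lets the chance of a chart-text hit depend on arm, through study-authored encounters and study-prompted PCP visits, mainly among participants interested in tapering. A raised intervention count is the more likely direction, but neither direction nor size can be derived until the indicators and the combination rule are stated. The relative risks in the table rest on assumed prevalence, sensitivity and false-positive rates.

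A reader might extend this to the trial's main conclusions. That is not supported: only the text component of one secondary outcome is affected, and this mechanism does not touch daily opioid dose, PEG or the separate patient-reported opioid problems outcome. It should be settled before any text is extracted.

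**What to change.** 1. Define the text indicators and how they combine with interview and questionnaire.
2. In the outcome definition, exclude text written by study staff from the search, identified by author ID or encounter type, and use the same date window in both arms.
3. Pre-specify an interview/questionnaire-only version as the key check. The filter leaves PCP notes from taper-prompted visits in place; only a version without text removes the arm-dependent component. Diagnosis codes should not be added to it, since Section 2 does not name them as a source.
4. Report an all-notes version as a further sensitivity analysis.
5. Add note text to the secondary-data table for both arms.

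The cost is a filter in the text query, two extra runs of a model already planned, and a few lines in the plan. No visit, treatment or sample size changes. The downside is that the filter removes text only in the intervention arm, so true problems recorded only in study-authored entries are missed, which could slightly favour the intervention. The interview/questionnaire-only version also has no value for participants who miss a survey. For both reasons the three versions should be reported together.
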